### **13.2.2 Safety**

#### **13.2.2.1 Adverse Events**

All AEs will be listed. The focus of AE summarization will be on treatment-emergent adverse events (TEAEs).

AEs will be classified using MedDRA with descriptions by System Organ Class and Preferred Term. The severity of AEs will be graded by the investigator according to the CTCAE, Version 4.03, whenever possible. If a CTCAE criterion does not exist for a specific type of AE, the grade corresponding to the appropriate adjective will be used by the investigator to describe the maximum intensity of the AE: Grade 1 (mild), Grade 2 (moderate), Grade 3 (severe), Grade 4 (life threatening), or Grade 5 (fatal). The relationship of the AE to the study drugs will be categorized as related or unrelated.

Summary tables will be presented to show the number of subjects reporting TEAEs by severity grade and corresponding percentages. A subject who

reports multiple TEAEs within the same Preferred Term (or System Organ Class) is counted only once for that Preferred Term (or System Organ Class) using the worst severity grade. AE descriptions will be presented in order of decreasing frequency for System Organ Class, and by decreasing frequency in the overall or total column for a given Preferred Term.

Separate listings and summaries will be prepared for the following types of AEs:

- Study-drug-related AEs
- AEs that are Grade  $\geq 3$ , 4, or 5 in severity
- AEs leading to study drug interruption and/or dose modification
- AEs leading to study drug discontinuation
- SAEs (with categorization of the primary reason that the AE is considered serious, eg, life-threatening, hospitalization)

### **13.2.2.2      Laboratory Evaluations**

All laboratory data will be listed. Summaries of laboratory data will be based on observed data and will be reported using conventional units. The focus of laboratory data summarization will be on treatment-emergent laboratory abnormalities. A treatment-emergent laboratory abnormality is defined as an abnormality that, compared to baseline, worsens by  $\geq 1$  grade in the period from the first study drug administration to 30 days after the last study drug administration. If baseline data are missing, then any graded abnormality (ie, an abnormality that is Grade  $\geq 1$  in severity) will be considered treatment-emergent.

Test data will be programmatically graded according to CTCAE severity grade, when applicable. For parameters for which a CTCAE scale does not exist, reference ranges from the laboratory will be used to determine programmatically if a laboratory parameter is below, within, or above the normal range for the subject's age, sex, etc.

Test data will be summarized in tables and may be summarized in figures showing values over time, if informative. Summary tables will be presented for each relevant assay to show the number of subjects by CTCAE severity grade with corresponding percentages. For parameters for which a CTCAE scale does not exist, the frequency of subjects with values below, within, and above the normal ranges will be summarized. Subjects will be characterized only once for a given assay, based on their worst severity grade observed during a period of interest (eg, during the study or during a cycle).

Shift tables for hematology and serum biochemistry will also be presented by showing change in CTCAE severity grade from baseline to each time point. For parameters for which a CTCAE scale does not exist, shift tables

will be presented showing change in results from baseline (normal, low and high [or abnormal]) to each time point (normal, low and high [or abnormal]). For selected variables of interest, tables may be prepared to show frequencies adjusted for baseline values; for these frequencies, subjects with the same or worse grade at baseline are not considered.

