### **1.5 Anti-Tumor T Cell Activity and Circadian Rhythms**

The immune response is an important predictor of glioma progression. Generally, the immune system and, more specifically, T lymphocytes are known to recognize tumor cells and target them for destruction. This action can initially restrain solid tumor growth. In support of this concept, glioma patients with lymphopenia have worse OS (Grossman et al, 2011). Chemotherapy such as TMZ that targets highly proliferative populations affects T cell populations in addition to tumor cells. T lymphocyte populations experience rapid proliferation, especially after exposure to activating antigen, like that released when a tumor cells dies from chemotherapy. However, the rapid proliferation of the T lymphocytes could be inhibited by chemotherapy. Glioma patients given TMZ and radiation experience lymphopenia after two months of treatment and lymphocyte counts remain depressed during the entire course of treatment (Grossman et al 2011). It would be ideal to specifically target the tumor cells while allowing the anti-tumor T cells to remain.

Like many other processes in the body, lymphocyte proliferation is dependent on circadian rhythms. Multiple studies have shown differential effects on lymphopenia depending on the time of day chemotherapy is administered. In a retrospective study, gemcitabine given at 9:00 am was less toxic to lymphocytes than gemcitabine given at 3:00 pm (Iwata K et al, 2011). In other studies, T cell progenitors in the bone marrow were found to be less proliferative at night. Due to the reduced proliferation, nighttime administration of docetaxel and irinotecan was found to reduce lymphocyte toxicity (Tampellini M et al 1998, Ohdo S 1997). This would suggest administering chemotherapy at a time of less T cell proliferation would prevent lymphopenia and potentially support the T cell mediated anti-tumor immune response as well as allow patients to stay on treatment schedule. This could be an addition mechanism by which patients could benefit from chronotherapy.

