#### **5.2 Study Assessments**

##### **5.2.1 Hematologic toxicity**

Hematologic toxicity will be assessed by standard blood collection. Blood draws will occur within the same 4-hour window each cycle for each patient to take into account peripheral blood T cell numbers. (Timing of draws need not be

synchronized across patients, only consistent for each individual patient.)

Hematologic toxicity will include grade 3 and 4 lymphopenia, thrombocytopenia, anemia and neutropenia. The criteria are summarized in the following chart:

Toxicity	Cell Type	Grade III criteria	Grade IV criteria
Lymphopenia	Lymphocytes	<500-200/mm 	<200/mm 
Leukopenia	Leukocytes	<2000-1000/mm 	<1000/mm 
Neutropenia	Neutrophils	<1000-500/mm 	<500/mm 
Thrombocytopenia	Platelets	<50,000-25,000/mm 	<25,000/mm 
Anemia	RBC (Hemoglobin)	<8.0-6.5 g/dL	<6.5 g/dL

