## 9.0 STUDY CALENDAR

	Baseline	Beginning of each cycle of TMZ	1 month after the last TMZ treatment 	Follow-up 
Informed consent	X			
ActTrust Condor Instrument watch		Continuously beginning after the signing of consent but no more than 2 weeks prior to initiation of TMZ		
Sleep Questionnaire	X	X	X	
FACT-Br	X	X	X	
Randomization	X			
Tracking of hematologic toxicity 		X		
Review of medical record				X

1. Every 3 months by chart review looking for progression and survival.

2. From SOC blood draws.

3. To coincide with the patient's SOC end of treatment follow up visit with treating physician.

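### Treatment-emergent laboratory abnormalities need a baseline grade, but no pre-dose blood count is scheduled, so lymphopenia present before monthly temozolomide can be reported as emergent

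*Combined protocol and SAP*

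**What the plan says.** Section 13.2.2.2 makes treatment-emergent abnormalities the focus of the laboratory summaries. An abnormality is emergent if it worsens by at least one grade from baseline "in the period from the first study drug administration to 30 days after the last study drug administration". Where there is no baseline, the rule is: "If baseline data are missing, then any graded abnormality (ie, an abnormality that is Grade $\geq 1$ in severity) will be considered treatment-emergent". The same section plans haematology shift tables "showing change in CTCAE severity grade from baseline to each time point". It does not say which sample is the baseline.

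In the calendar (9.0), the row "Tracking of hematologic toxicity" is marked only at the beginning of each cycle; its Baseline cell is empty. The footnote gives the source: "From SOC blood draws". In 10.0 the Hematologic Toxicity Form is monthly and is not among the forms due before treatment.

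Section 5.2.1 keeps each patient's draws within one 4-hour window from cycle to cycle but does not place the draw before the dose. Across patients, "Timing of draws need not be" synchronised. Sections 4.4 and 5.1 set dosing before 10:00 or after 20:00.

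Section 1.5 reports that glioma patients given temozolomide and radiation become lymphopenic and that "lymphocyte counts remain depressed during the entire course of treatment".

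**The concern.** The missing-baseline rule in effect treats an unknown starting grade as normal. That does little harm when baselines are rarely missing and patients start with normal counts. Here the plan schedules no baseline count, and many patients may start monthly temozolomide after chemoradiotherapy, with low lymphocytes. Lymphopenia carried in from earlier treatment would then be labelled as arising on study.

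The randomised factor is the clock time of the dose, so whether a first-day count is pre-dose may itself depend on the arm. Section 2.0 says the study collects pilot data for later chronotherapy studies, so a false level or a false difference in emergent lymphopenia could be carried into their design. The shift tables face a simpler problem: without a baseline grade there is nothing to shift from.

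**Working it through.** The plan gives no figure on this point to reproduce, so the first step is to compare the sections.

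1. **Is a pre-dose count required?** The calendar marks consent, randomisation, FACT-Br and the sleep questionnaire at Baseline, but not haematology. The form schedule agrees. An On-Study Form is due before treatment, but its contents are not described. Eligibility (3.1, 3.2) requires no blood count. Section 5.2.1 sets a window, not an order relative to the dose. So nothing requires one.

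2. **What happens to a patient without one?** Under 13.2.2.2, any Grade 1 or higher value from the first dose onward is emergent. A patient with stable prior lymphopenia is counted; with a recorded baseline, that patient would be counted only after worsening by a grade.

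3. **Can this differ by arm?** A daytime draw on the first dosing day precedes a dose taken after 20:00 and can serve as baseline. The same draw can follow a dose taken before 10:00, and then lies inside the emergent window.

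**Inputs for size.** From the documents: 40 patients (13.0) randomised 1:1 (4.4), so about n = 40/2 = 20 per arm. Assumed, because the documents give no values:
- f, share of morning patients without a pre-dose count: 10-50%
- p, share with graded lymphopenia before the first dose: 30-70%
- w, share of those who truly worsen by at least one grade: 25-50%

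Prior lymphopenia is taken to persist to at least one post-dose count, and the evening arm's first draw is taken as pre-dose.

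**Morning-arm patients falsely counted** = n × f × p × (1 − w)
- Low: 20 × 0.10 × 0.30 × (1 − 0.50) = 0.3 patients (1.5 percentage points)
- High: 20 × 0.50 × 0.70 × (1 − 0.25) = 5.25 patients (about 26 points)

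The factor (1 − w) is needed because a patient who truly worsens is emergent under either rule.

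**Illustration.** Take p = 40%, w = 40%, 40% emergent among patients without prior lymphopenia, and no true arm difference.
- Baseline known for all: 0.4 × 0.4 + 0.6 × 0.4 = 40% in each arm.
- Half the morning arm without baseline: 0.4 × (0.5 + 0.5 × 0.4) + 0.6 × 0.4 = 52%, against 40% in the evening arm; a false difference of 12 points.
- Baseline missing for everyone: 0.4 × 1 + 0.6 × 0.4 = 64% in both arms; no false difference, but the level is 24 points too high.
- Baseline captured for everyone: no excess of either kind.

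For scale, with 20 per arm and 40% in each, the 95% confidence interval half-width for the difference is 1.96 × √(2 × 0.4 × 0.6/20) ≈ 0.30, or 30 points.

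**The case against.** The strongest reply is that an empty Baseline cell in a toxicity-tracking row means only that toxicity is not tracked before treatment. Standard care may well supply a count before the first dose, and 13.2.2.2 treats a missing baseline as the exception. That is fair: the documents do not show that pre-dose counts are absent. They do not require that one be collected or identified either, and the analysis depends on it.

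A reader might infer that the morning arm is systematically penalised. The documents do not support that. It needs a first count on the first dosing day, taken after a morning dose, with no earlier count captured, and that same visit's count accepted as baseline only in the evening arm. None of this is stated. If the first-cycle count serves as baseline in both arms, or baseline is missing equally in both, no between-arm bias arises by this route.

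A reader might also infer that secondary objective 1 is distorted. It is not: 2.2 and 13.1.2 count patients against the grade 3-4 thresholds of 5.2.1, with no treatment-emergent restriction. Those counts cannot separate prior from new cytopenia, but this rule does not alter them. Nor is the default stated for shift tables; for these, 13.2.1 by default shows missing observations as a separate category.

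Finally, counting abnormalities of unknown origin as emergent is a cautious safety convention. That stands, and is a reason to keep it as a fallback. Section 1.5 gives no prevalence, and 3.1 also admits recurrent and high-risk grade II disease, so recent chemoradiotherapy cannot be presumed for every patient.

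**Conclusion.** The point holds as a gap between analysis and data collection: 13.2.2.2 needs a baseline grade that 9.0 and 10.0 do not collect, and its default can then report existing lymphopenia as emergent. The treatment-emergent laboratory summaries are exposed to this, and the shift tables may lack a starting grade.

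Inflation in both arms and a difference between arms are both possible; the documents do not show which would occur, or how often. The range of about 0.3 to 5.25 of 20 morning-arm patients rests wholly on the assumed f, p and w, and falls to zero if every patient has a captured pre-dose count. The analyses are descriptive and the primary endpoint is compliance, so no error rate or primary conclusion is affected. The correction is still worth making, because it is cheap and these summaries are meant to inform later trials.

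**What to change.** - **Sections 9.0 and 10.0:** add chart abstraction of the last standard-of-care blood count before the first temozolomide dose, with the date and clock time of that draw and of the first dose.
- **Section 13.2.2.2:** define that value as baseline in both arms, for the emergent definition and the shift tables.
- **Patients still without a pre-dose count:** keep the present default, report their number by arm, and give the treatment-emergent table with and without them.

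Dropping the default altogether is less attractive. With f at 10-50%, 2 to 10 of 20 morning-arm patients would have their abnormalities left out of the emergent table, which could hide genuine new events, possibly in one arm only.

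The cost is one abstracted count per patient with its times, and one extra table. No extra blood draw is needed.

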We would like to thank the Alvin J. Siteman Cancer Center at Washington University School of Medicine and Barnes-Jewish Hospital in St. Louis, Missouri, for the use of the Clinical Trials Core which provided protocol development service. The Siteman Cancer Center is supported in part by an NCI Cancer Center Support Grant #P30 CA91842.

## Appendix A: Karnofsky Performance Status Scale

Definition	Score	Criteria
Able to carry on normal activity and to work; no special care needed.	100	Normal, no complaints; no evidence of disease.
	90	Able to carry on normal activity; minor signs or symptoms of disease.
	80	Normal activity with effort; some signs or symptoms of disease.
Unable to work; able to live at home and care for most personal needs; varying amount of assistance needed.	70	Cares for self; unable to carry on normal activity or to do active work.
	60	Requires occasional assistance, but is able to care for most personal needs.
	50	Requires considerable assistance and frequent medical care.
Unable to care for self; requires equivalent of institutional or hospital care; disease may be progressing rapidly.	40	Disabled; requires special care and assistance.
	30	Severely disabled; hospital admission is indicated although death not imminent.
	20	Very sick; hospital admission necessary; active supportive treatment necessary.
	10	Moribund; fatal processes progressing rapidly.
	0	Dead.

Oxford Textbook of Palliative Medicine, Oxford University Press. 1993;109.

## Appendix B: FACT-BR Quality of Life Survey

Below is a list of statements that other people with your illness have said are important. **Please circle or mark one number per line to indicate your response as it applies to the past 7 days.**

			Not at all	A little bit	Some- what	Quite a bit	Very much
	PHYSICAL WELL-BEING						
GP1	I have a lack of energy .....	0	1	2	3	4	
GP2	I have nausea .....	0	1	2	3	4	
GP3	Because of my physical condition, I have trouble meeting the needs of my family .....	0	1	2	3	4	
GP4	I have pain .....	0	1	2	3	4	
GP5	I am bothered by side effects of treatment .....	0	1	2	3	4	
GP6	I feel ill .....	0	1	2	3	4	
GP7	I am forced to spend time in bed .....	0	1	2	3	4	
	SOCIAL/FAMILY WELL-BEING		Not at all	A little bit	Some- what	Quite a bit	Very much
GS1	I feel close to my friends .....	0	1	2	3	4	
GS2	I get emotional support from my family .....	0	1	2	3	4	
GS3	I get support from my friends .....	0	1	2	3	4	
GS4	My family has accepted my illness .....	0	1	2	3	4	
GS5	I am satisfied with family communication about my illness .....	0	1	2	3	4	
GS6	I feel close to my partner (or the person who is my main support) .....	0	1	2	3	4	
Q1	Regardless of your current level of sexual activity, please answer the following question. If you prefer not please mark this box  and go to the next section.						
GS7	I am satisfied with my sex life .....	0	1	2	3	4	

**Please circle or mark one number per line to indicate your response as it applies to the past 7 days.**

**EMOTIONAL WELL-BEING**

		Not at all	A little bit	Some- what	Quite a bit	Very much
GE1	I feel sad .....	0	1	2	3	4
GE2	I am satisfied with how I am coping with my illness.....	0	1	2	3	4
GE3	I am losing hope in the fight against my illness.....	0	1	2	3	4
GE4	I feel nervous.....	0	1	2	3	4
GES	I worry about dying.....	0	1	2	3	4
GE6	I worry that my condition will get worse .....	0	1	2	3	4

**FUNCTIONAL WELL-BEING**

		Not at all	A little bit	Some- what	Quite a bit	Very much
GF1	I am able to work (include work at home) .....	0	1	2	3	4
GF2	My work (include work at home) is fulfilling.....	0	1	2	3	4
GF3	I am able to enjoy life.....	0	1	2	3	4
GF4	I have accepted my illness.....	0	1	2	3	4
GF5	I am sleeping well .....	0	1	2	3	4
GF6	I am enjoying the things I usually do for fun .....	0	1	2	3	4
GF7	I am content with the quality of my life right now.....	0	1	2	3	4

**Please circle or mark one number per line to indicate your response as it applies to the past 7 days.**

ADDITIONAL CONCERNS		Not at all	A little bit	Some - what	Quit e a bit	Very muc h
Br1	I am able to concentrate .....	0	1	2	3	4
Br2	I have had seizures (convulsions) .....	0	1	2	3	4
Br3	I can remember new things .....	0	1	2	3	4
Br4	I get frustrated that I cannot do things I used to.....	0	1	2	3	4
Br5	I am afraid of having a seizure (convulsion).....	0	1	2	3	4
Br6	I have trouble with my eyesight.....	0	1	2	3	4
Br7	I feel independent .....	0	1	2	3	4
NTX6	I have trouble hearing.....	0	1	2	3	4
Br8	I am able to find the right word(s) to say what I mean .....	0	1	2	3	4
Br9	I have difficulty expressing my thoughts .....	0	1	2	3	4
Br10	I am bothered by the change in my personality .....	0	1	2	3	4
Br11	I am able to make decisions and take responsibility .....	0	1	2	3	4
Br12	I am bothered by the drop in my contribution to the family .....	0	1	2	3	4
Br13	I am able to put my thoughts together.....	0	1	2	3	4
Br14	I need help in caring for myself (bathing, dressing, eating, etc.) .....	0	1	2	3	4
Br15	I am able to put my thoughts into action.....	0	1	2	3	4
Br16	I am able to read like I used to .....	0	1	2	3	4
Br17	I am able to write like I used to.....	0	1	2	3	4
Br18	I am able to drive a vehicle (my car, truck, etc.).....	0	1	2	3	4
Br19	I have trouble feeling sensations in my arms, hands, or legs .....	0	1	2	3	4
Br20	I have weakness in my arms or legs.....	0	1	2	3	4
Br21	I have trouble with coordination .....	0	1	2	3	4
An10	I get headaches .....	0	1	2	3	4

## Appendix C: Quality of Sleep Questionnaire

1. What time do you typically go to bed on weekdays? \_\_\_\_:\_\_\_\_ am/pm
2. How long does it take you to fall asleep? \_\_\_\_\_(hours/min)
3. What time do you typically wake up on weekdays? \_\_\_\_:\_\_\_\_ am/pm
  - a. Do you use an alarm clock/wake up call? YES NO
  - b. Do you feel refreshed upon waking up? YES NO
4. What time do you typically go to bed on the weekend/days off? \_\_\_\_:\_\_\_\_ am/pm
5. How long does it take you to fall asleep? \_\_\_\_\_(hours/min)
6. What time do you wake up on the weekend/days off? \_\_\_\_:\_\_\_\_ am/pm
  - a. Do you use an alarm clock/wake up call? YES NO
  - b. Do you feel refreshed upon waking up? YES NO
7. How many times do you wake up on a typical night? \_\_\_\_\_
8. Do you have difficulty falling back to sleep? YES NO
9. Check typical causes for awakening at night:
  - a. Snoring
  - b. Pain
  - c. Full bladder
  - d. Noise
  - e. Nightmares
  - f. Worry
  - g. Thirst/hunger
  - h. Bed partner/kids/pets
  - i. Night sweats
  - j. Headache
  - k. Heartburn
  - l. Choking/gasping

Please list other causes: \_\_\_\_\_

10. Do you nap intentionally? YES NO
  - a. If yes, how many days per week? \_\_\_\_\_
  - b. What time of day? \_\_\_\_\_
  - c. How long are naps? \_\_\_\_\_
  - d. Do you feel refreshed upon waking up from the nap? YES NO

11. Do you have problems getting to sleep or staying asleep? YES NO

12. Please rate the current, (i.e. the last 2 weeks) SEVERITY of your insomnia problem(s):

	None	Mild	Moderate	Severe	Very
1. Difficulty falling asleep	0	1	2	3	4
2. Difficulty staying asleep	0	1	2	3	4
3. Problem waking up too early	0	1	2	3	4

	Very Satisfied				Very Dissatisfied
1. How SATISFIED or DISSATISFIED are you with your current sleeping pattern?	0	1	2	3	4
	Not at all Interfering	A Little	Somewhat	Much	Very Much Interfering
2. To what extent do you consider your sleep problem to INTERFERE with your daily functioning? (i.e., daytime fatigue, ability to function at work/daily chores, concentration, memory, mood, etc.)	0	1	2	3	4
	Not at all Noticeable	Barely	Somewhat	Much	Very Noticeable
3. How NOTICEABLE to others do you think your sleeping problem is in terms of impairing the quality of your life?	0	1	2	3	4
	Not at all	A Little	Somewhat	Much	Very Much
4. How WORRIED or DISTRESSED are you about your current sleep problem?	0	1	2	3	4
